4.2 Exclusion Criteria

Patients meeting **any** of the following criteria will be excluded from participation in the study:

- 1. Prior treatment with an anti-PD1 or anti-PD-L1 antibody
- 2. Eligible, to participate in a clinical trial of an alternative anticancer therapy targeting their disease which is open to accrual in France.
- 3. Concurrent steroid medication at a dose greater than prednisone 10 mg/day or equivalent (Appendix 7). For patients with germ-cell cancer, PCNSL concurrent steroid medication at a dose greater than prednisone 20 mg/day or equivalent.
- 4. Has active autoimmune disease that has required systemic treatment in the past 2 years (i.e. with use of disease modifying agents, corticosteroids or immunosuppressive drugs).

- Replacement therapy (eg., thyroxine, insulin, or physiologic corticosteroid replacement therapy for adrenal or pituitary insufficiency, etc.) is not considered a form of systemic treatment.
- 5. History of (non-infectious) pneumonitis that required steroids, or current pneumonitis.
- 6. History of severe hypersensitivity reaction to any monoclonal antibody therapy
- 7. Radiotherapy (except for brain and extremities) within 21 days prior to the first administration of IP.
- 8. Treatment with other investigational drugs or participation in another clinical trial within 21 days prior to the first administration of IP or concomitantly with the trial.
- 9. Has known symptomatic central nervous system (CNS) metastases. Patients with previously treated brain metastases may participate provided they are stable (without evidence of progression by imaging for at least four weeks prior to the first dose of trial treatment and any neurologic symptoms have returned to baseline), have no evidence of new or enlarging brain metastases, and are not using steroids for at least 7 days prior to trial treatment.
- 10. Has known carcinomatous meningitis or a history of leptomeningeal disease, except for patients with primary CNS lymphoma.
- 11. Serum creatinine > 1.5 xULN or glomerular filtration rate (GFR) < 50 ml/min.
- 12. Other malignancies within the past 5 years other than basal cell skin cancer or *in situ* carcinoma of the cervix.
- 13. Active serious infections in particular if requiring systemic antibiotic or antimicrobial therapy.
- 14. Active or chronic hepatitis B, hepatitis C and/or human immunodeficiency virus (HIV) infection (HIV 1/2 antibodies), or a known history of active *Tuberculosis bacillus*.

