5.3.2 Treatment Interruption

Treatment with pembrolizumab may be interrupted at the Investigators discretion depending on the type and severity of the toxicity encountered. Treatment is to be interrupted in the event of any of the toxicities listed in Table 3.

In the event of treatment interruption due to toxicity of more than 56 days, the decision to restart treatment or not should be discussed and agreed between the Investigator and Sponsor.

Table 3. Dose Modification and Toxicity Management Guidelines for Immune-related Adverse Events Associated with Pembrolizumab

General instructions:

- 1. Corticosteroid taper should be initiated upon AE improving to Grade 1 or less and continue to taper over at least 4 weeks.
- 2. For situations where pembrolizumab has been withheld, pembrolizumab can be resumed after AE has been reduced to Grade 1 or 0 and corticosteroid has been tapered. Pembrolizumab should be permanently discontinued if AE does not resolve within 12 weeks of last dose or corticosteroids cannot be reduced to ≤10 mg prednisone or equivalent per day within 12 weeks.
- **3.** For severe and life-threatening irAEs, IV corticosteroid should be initiated first followed by oral steroid. Other immunosuppressive treatment should be initiated if irAEs cannot be controlled by corticosteroids.

Toxicity	Grade*	Action taken with pembrolizumab	Toxicity management	Monitor and follow-up
Pneumonitis	Grade 2 Grade 3 or 4, or recurrent Grade 2	Withhold Permanently discontinue	Administer corticosteroids (initial dose of 1-2 mg/kg prednisone or equivalent) followed by taper	 Monitor participants for signs and symptoms of pneumonitis Evaluate participants with suspected pneumonitis with radiographic imaging and initiate corticosteroid treatment Add prophylactic antibiotics for opportunistic infections

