5.9 Concomitant Treatments

All medications and therapies taken by the patients or administered to the patients at the onset of trial and all medication given in addition to the IP during the trial are considered as concomitant medications.

Medications or vaccinations specifically prohibited in the exclusion criteria or Section 5.9.2 are not allowed during the ongoing trial. If there is a clinical indication requiring treatment with one of these medications, discontinuation from trial therapy may be required. The investigator should discuss any questions regarding this with the Sponsor. The final decision on any supportive therapy or vaccination rests with the investigator and/or the subject's primary physician.

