5.9.2 Prohibited Concomitant Treatments

Subjects are prohibited from receiving the following therapies during the Screening and Treatment Phase (including retreatment for post-complete response relapse) of this trial:

- Antineoplastic systemic chemotherapy or biological therapy
- Immunotherapy not specified in this protocol
- Chemotherapy not specified in this protocol
- Investigational agents other than pembrolizumab
- Radiation therapy
 - Palliative radiation therapy to a single symptomatic lesion or to the brain may be allowed, provided the lesion is not a target lesion for RECIST v1.1 evaluation and the need for therapy does not equate to progressive disease. Patients with PD must discontinue study treatment.
- Live vaccines within 30 days prior to the first dose of IP and while participating in the trial. Examples of live vaccines include, but are not limited to, the following: measles, mumps, rubella, varicella/zoster, yellow fever, rabies, Bacillus Calmette–Guérin (BCG), and typhoid vaccine
- Systemic glucocorticoids at a dose greater than prednisone 10 mg/day or equivalent (Appendix 4). The use of physiologic doses of corticosteroids may be approved after consultation with the Sponsor.
- Other medications described in the exclusion criteria (Section 4.2)

Subjects who, in the assessment by the investigator, require the use of any of the aforementioned treatments for clinical management should be removed from the trial. Subjects may receive other medications that the investigator deems to be medically necessary.

There are no prohibited therapies during the LTFU Phase.

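### Section 5.9.2 bars steroids above 10 mg/day and directs removal from the trial, with no exception for the steroid courses Table 3 orders or for the germ-cell and PCNSL patients criterion 3 admits on up to 20 mg/day

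*Protocol*

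**What the plan says.** **Section 5.9.2** lists treatments prohibited during Screening and Treatment, including retreatment. One entry is "Systemic glucocorticoids at a dose greater than prednisone 10 mg/day or equivalent (Appendix 4"). The entry allows physiologic doses after consultation with the sponsor and nothing else. The section then says that subjects who, in the investigator's assessment, "require the use of any of the aforementioned treatments for clinical management should be removed from the trial".

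**Section 5.9**, the parent section, states that "Medications or vaccinations specifically prohibited in the exclusion criteria or Section 5.9.2 are not allowed during the ongoing trial". If such a treatment is clinically indicated, it says only that "discontinuation from trial therapy may be required". It leaves the final decision on supportive therapy to the investigator or the patient's primary physician.

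**Section 4.2, exclusion criterion 3** (repeated in the synopsis) sets a general entry limit of 10 mg/day, with a separate limit for two cohorts: "For patients with germ-cell cancer, PCNSL concurrent steroid medication at a dose greater than prednisone 20 mg/day or equivalent".

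**Section 5.3.2, Table 3** directs prednisone at 0.5-1 mg/kg or 1-2 mg/kg for several immune-related events for which pembrolizumab is to be withheld. Its general instructions say "Corticosteroid taper should be initiated upon AE improving to Grade 1 or less and continue to taper over at least 4 weeks" and "pembrolizumab can be resumed after AE has been reduced to Grade 1 or 0 and corticosteroid has been tapered". They require permanent discontinuation if the event has not resolved, or the dose is not down to 10 mg/day or less, within 12 weeks. Section 5.10.1 refers to the same courses and expects that several tapers may be needed.

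**The concern.** Two groups of patients are caught by a rule that other parts of the protocol contradict.

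The first is patients with an immune-related event who are treated exactly as Table 3 directs. They need a dose well above 10 mg/day, so 5.9.2 read literally removes them from the trial, while Table 3 keeps them in and lets them resume.

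The second is germ-cell or PCNSL patients on more than 10 and up to 20 mg/day. They are eligible under criterion 3 but already in breach of 5.9.2 during Screening.

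The stated consequence also differs. Stopping study drug, perhaps (5.9), is not the same act as removal from the trial (5.9.2). Applied as written, 5.9.2 would take eligible or correctly managed patients out of a trial intended for people with no other treatment option.

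**Working it through.** The plan gives no figure to reproduce. The check compares the texts and then sizes the conflict.

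**1. Does every dosed Table 3 course breach the ceiling?** The lowest stated dose is 0.5 mg/kg (Grade 2 AST/ALT or bilirubin). It exceeds 10 mg/day for any patient above 10 / 0.5 = 20 kg, so for practical purposes every course with a stated dose does. At an assumed 70 kg:
- lowest: 70 × 0.5 = 35 mg/day, 3.5 times the ceiling;
- highest: 70 × 2 = 140 mg/day, 14 times the ceiling.

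**2. For how long?** Take the 4-week minimum taper as linear to zero (an assumption). Days above 10 mg/day during the taper alone are 28 × (1 − 10/start dose):
- from 35 mg: 28 × (1 − 10/35) = 20 days;
- from 140 mg: 28 × (1 − 10/140) = 26 days.

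**3. How many patients?** Use Table 1 (section 1.1.3.2, n = 2117, melanoma and NSCLC). Count only grades that Table 3 withholds, may resume, and treats with a stated steroid dose.

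| Event | Grades counted | Rate |
|---|---|---|
| Pneumonitis | 2 | 0.9% |
| Colitis | 2-3 | 0.4-2.1% |
| Hepatitis | 2 | 0.1% |
| Nephritis | 2 | 0.1% |

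The colitis row of Table 1 is internally inconsistent: all grades 1.7%, but Grade 2 is 0.4% and Grade 3 is 1.7%. Three readings follow:
- grade columns as printed: 0.4 + 1.7 = 2.1%;
- all-grades figure correct: at most 1.7 − 0.1 (Grade 4) = 1.6%;
- Grade 3 entry is the error: possibly as low as about 0.4%.

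Totals:
- low: 0.9 + 0.4 + 0.1 + 0.1 = 1.5%; × 350 = 5.25, about 5 patients;
- middle: 0.9 + 1.6 + 0.1 + 0.1 = 2.7%; × 350 = 9.45, about 9;
- high: 0.9 + 2.1 + 0.1 + 0.1 = 3.2%; × 350 = 11.2, about 11.

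These totals leave out events for which Table 3 orders steroids without a dose, such as Grade 2 hypophysitis.

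**4. Entry limit.** Criterion 3 lets in germ-cell and PCNSL patients at >10 to 20 mg/day, and 5.9.2 forbids that range from Screening onward. The share of such patients is not stated. Each 10% assumed is 2-5 patients in a cohort of 20-50. If all 50 extra places under amendment 6 went to PCNSL (50 + 50 = 100), it would be 10.

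**5. Cross-reference.** 5.9.2 points to Appendix 4 for steroid equivalents. Appendix 4 is the Lugano classification; the equivalents are in Appendix 7, which criterion 3 cites correctly.

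**The case against.** The best defence is that Table 3 and 5.10.1 are the specific instructions for immune-related events and 5.9.2 is general, so a sensible site would follow Table 3. Section 5.9 supports this: discontinuation is only a possibility, questions go to the sponsor, and the investigator decides on supportive therapy. That makes widespread wrongful removal unlikely. It does not settle the text. Section 5.9.1 excludes the 5.9.2 list from the investigator's freedom to prescribe, 5.9.2 writes out exceptions where it wants them (palliative radiotherapy, physiologic steroids), and nothing in 5.9 cancels the removal sentence.

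On the entry limit, the defence is partly right. Not excluding a dose at entry is not permission to continue it on treatment, and a patient at or below 10 mg/day satisfies both rules. A reader might infer that the 5.9.2 entry "Other medications described in the exclusion criteria (Section 4.2") brings the 20 mg/day allowance into the treatment period. It does not: glucocorticoids have their own entry just above, so the word Other does not naturally reach them. A reader might also take the PCNSL criteria in Appendix 3, where steroid dose does not affect a partial response, as permitting higher doses. That is a scoring rule and sets no permitted dose. What stands is the patient who is eligible on >10 to 20 mg/day and in breach during Screening.

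A reader might further infer that patients removed before Day 84 become non-responders and depress the response rate or trigger futility. That would require equating removal under 5.9.2 with withdrawal from the study in 3.1.1 and 10.2.1. Section 6.1 names death and withdrawal of consent as treatment failure, and 10.4 adds loss to follow-up. Section 7.4.2 and flow-chart footnote 15 keep tumour assessments going after a stop for reasons other than progression. The documents do not support the inference.

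**Conclusion.** The contradiction is in the current text and should be fixed. Section 5.9.2 prohibits, with removal from the trial as the consequence, steroid courses that Table 3 and 5.10.1 order. It also conflicts during Screening with the entry allowance for two cohorts, states a different consequence from 5.9, and cites the wrong appendix.

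The Table 3 conflict concerns roughly 1.5-3.2% of patients, about 5-11 of 350. This assumes that melanoma/NSCLC rates carry over to these cancers and that events fall in separate patients. Most of the width comes from the inconsistent colitis row. The entry conflict cannot be sized from the protocol. The matter is one of patient management and clear instructions to sites; no effect on the primary endpoint or the futility looks is claimed.

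**What to change.** In 5.9.2:
- Exempt steroid courses given for immune-related events under Table 3 and 5.10.1, and for infusion reactions under Table 4.
- For steroid use, replace removal from the trial with a decision on study drug only, with disease assessments continuing under 7.2.8 and 7.4.2.
- Correct the reference to Appendix 7.
- Align the germ-cell/PCNSL limit with criterion 3 at least through Screening and entry.

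The sponsor must then choose the on-treatment limit for those two cohorts, because the protocol does not settle it. If 20 mg/day is intended, say so and amend Table 3's rule of 10 mg/day or less within 12 weeks for them, for example to a return to the permitted baseline dose. Otherwise a PCNSL patient stable on 15 mg/day who has an immune event would have to stop permanently. If 10 mg/day is intended, state by when the dose must fall to that level.

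The cost is a wording change in 5.9.2, plus Table 3 if 20 mg/day is chosen. No new data or visits are needed. If classed as substantial, it needs ANSM and ethics committee approval under 14.5 and can go in with the next amendment.

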5.10 Rescue Medication

5.10.1 Supportive Care Guidelines

Subjects should receive appropriate supportive care measures as deemed necessary by the treating Investigator. Suggested supportive care measures for the management of AEs with potential immunologic etiology are outlined in Table 3 (Section 5.3). Where appropriate, these guidelines include the use of oral or intravenous treatment with corticosteroids as well as additional anti-inflammatory agents if symptoms do not improve with administration of corticosteroids.

Note that several courses of steroid tapering may be necessary as symptoms may worsen when the steroid dose is decreased. For each disorder, attempts should be made to rule out other causes such as metastatic disease or bacterial or viral infection, which might require additional supportive care. It may be necessary to perform conditional procedures such as bronchoscopy, endoscopy, or skin photography as part of evaluation of the event. The treatment guidelines are intended to be applied when the Investigator determines the events to be related to pembrolizumab. If after the evaluation the event is determined not to be related, the Investigator does not need to follow the treatment guidance below.

Management of Infusion Reactions:

Signs and symptoms usually develop during or shortly after drug infusion and generally resolve completely within 24 hours of completion of infusion. Table 4 below shows treatment guidelines for subjects who experience an infusion reaction associated with administration of pembrolizumab.

Overdose:

For purposes of this trial, an overdose of pembrolizumab will be defined as any dose of 1,000 mg or greater (≥5 times the indicated dose). No specific information is available on the treatment of overdose of pembrolizumab. Appropriate supportive treatment should be provided if clinically indicated. In the event of overdose, the subject should be observed closely for signs of toxicity. Appropriate supportive treatment should be provided if clinically indicated.

Table 4. **Infusion Reaction Treatment Guidelines**

Grade ⁽¹⁾	Treatment	Premedication at subsequent dosing
Grade 1 Mild reaction; infusion interruption not indicated; intervention not indicated	Increase monitoring of vital signs as medically indicated until the patient is deemed medically stable in the opinion of the investigator.	None
Grade 2 Requires infusion interruption but responds promptly to symptomatic treatment (e.g., antihistamines, NSAIDS, narcotics, IV fluids); prophylactic medications indicated for < =24 hrs	Stop Infusion and monitor symptoms. Additional appropriate medical therapy may include but is not limited to: IV fluids Antihistamines NSAIDS Acetaminophen Narcotics Increase monitoring of vital signs as medically indicated until the patient is deemed medically stable in the opinion of the investigator. If symptoms resolve within one hour of stopping drug infusion, the infusion may be restarted at 50% of the original infusion rate (e.g., from 100 mL/hr to 50 mL/hr). Otherwise dosing will be held until symptoms resolve and the patient should be premedicated for the next scheduled dose. Patients who develop Grade 2 toxicity despite adequate premedication should be permanently discontinued from further trial treatment administration.	Patient may be premedicated 1.5h (± 30 minutes) prior to infusion of pembrolizumab (MK-3475) with: Diphenhydramine 50 mg po (or equivalent dose of antihistamine). Acetaminophen 500-1000 mg po (or equivalent dose of antipyretic).
Grades 3 or 4 Grade 3: Prolonged (i.e., not rapidly responsive to symptomatic medication and/or brief interruption of infusion); recurrence of symptoms following initial improvement; hospitalization indicated for other clinical sequelae (e.g., renal impairment, pulmonary infiltrates)	Stop Infusion. Additional appropriate medical therapy may include but is not limited to: IV fluids Antihistamines NSAIDS Acetaminophen Narcotics Oxygen Pressors Corticosteroids Epinephrine	No subsequent dosing
Grade 4: Life-threatening; pressor or ventilatory support indicated	Increase monitoring of vital signs as medically indicated until the patient is deemed medically stable in the opinion of the investigator. Hospitalization may be indicated. Patient is permanently discontinued from further trial treatment.	

NSAIDS= Nonsteroidal anti-inflammatory drugs (1) NCI-CTCAE version 4.1

Appropriate resuscitation equipment should be available in the room and a physician readily available during the period of drug administration.

Protocol n° UC-0105/1612 - version n°10.0, November 22, 2020

5.11 Diet/Activity/Other Considerations

5.11.1 Diet

Patients should maintain a normal diet unless modifications are required to manage an AE such as diarrhoea, nausea or vomiting.

5.11.2 Contraception

Patients should be informed that pembrolizumab may have adverse effects on a foetus *in utero*. Furthermore, it is not known if pembrolizumab has transient adverse effects on the composition of sperm. All patients of reproductive potential must agree to use (or have their partner use) a medically accepted form of contraception¹ during heterosexual activity, or practice abstinence² from heterosexual activity for the period beginning at least 14 days prior to their first IP administration, during the treatment period, and for at least 5 months after their last dose of IP for female patients, and 7 months after the last administration of IP for male patients. If there is any question that a patient of reproductive potential will not reliably comply with the requirements for contraception, that patient should not be entered into the study.

Acceptable methods of contraception¹ are:

- Single method (one of the following is acceptable):
 - o intrauterine device
 - o vasectomy of a female subject's male partner
 - o contraceptive rod implanted into the skin
- Combination method (requires use of two of the following):
 - o diaphragm with spermicide (cannot be used in conjunction with cervical cap/spermicide)
 - o cervical cap with spermicide (nulliparous women only)
 - o contraceptive sponge (nulliparous women only)
 - o male condom or female condom (cannot be used together)
 - hormonal contraceptive: oral contraceptive pill (oestrogen/progestin pill or progestinonly pill), contraceptive skin patch, vaginal contraceptive ring, or subcutaneous contraceptive injection

For this trial, male subjects will be considered to be of non-reproductive potential if they have azoospermia (whether due to having had a vasectomy or due to an underlying medical condition). Female subjects will be considered of non-reproductive potential if they are either:

- 1. Postmenopausal (defined as at least 12 months with no menses without an alternative medical cause; in women < 45 years of age a high follicle stimulating hormone (FSH) level in the postmenopausal range may be used to confirm a post-menopausal state in women not using hormonal contraception or hormonal replacement therapy. In the absence of 12 months of amenorrhea, a single FSH measurement is insufficient.);
- 2. OR, have had a hysterectomy and/or bilateral oophorectomy, bilateral salpingectomy or bilateral tubal ligation/occlusion, at least 6 weeks prior to screening;
- 3. OR, have a congenital or acquired condition that prevents childbearing.

² Abstinence (relative to heterosexual activity) can be used as the sole method of contraception if it is consistently employed as the subject's preferred and usual lifestyle and if considered acceptable by local regulatory agencies and ethics committees. Periodic abstinence (e.g., calendar, ovulation, sympto-thermal, post-ovulation methods, etc.) and withdrawal are not acceptable methods of contraception.

Protocol n° UC-0105/1612 - version n°10.0, November 22, 2021

DOC43 Protocol ME EN v1.0 05-09-2014

¹ If one of the contraceptive methods listed is restricted by local regulations/guidelines, then it does not qualify as an acceptable method of contraception for subjects participating at sites in this country/region.

5.11.3 Use in Pregnancy

If a patient inadvertently becomes pregnant while on treatment with pembrolizumab, the patient will immediately be removed from the study. The Investigator will contact the patient at least monthly and document the patient's status until the pregnancy has been completed or terminated. The outcome of the pregnancy will be reported to the Sponsor and to the IP license holder without delay and within 24 hours to the Sponsor and within 2 working days to the IP license holder if the outcome is a serious adverse experience (e.g., death, abortion, congenital anomaly, or other disabling or life-threatening complication to the mother or newborn). The Investigator will make every effort to obtain permission to follow the outcome of the pregnancy and report the condition of the foetus or newborn to the Sponsor. If a male subject impregnates his female partner the study personnel at the site must be informed immediately and the pregnancy reported to the Sponsor and to the IP license holder and followed as described above.

